(Tzefos 2009, AHRP reference guide) Additionally, fesoterodine has been compared to tolterodine, and may show greater efficacy. (Tzefos 2009) In fact, fesoterodine tends to have low incidence of dry mouth, and moderate incidence of constipation compared to other anti-muscarinics, making it a well-tolerated and appropriate first choice for most patients.(Ellsworth 2014) Low CNS penetration may also potentiate fewer CNS side effects.(Ellsworth2014) Additionally, our previously presented data on the potential positive effects of anticholinergic medication on physical activity was collected using fesoterodine, so there is a precedent for using this anticholinergic in a study examining changes in activity and sedentary behavior. Therefore, fesoterodine, the drug used in this study, is an appropriate medication for routine and standard care of overactive bladder. Fesoterodine is being supplied by Pfizer for the use of this study. As part of routine clinical care at the urogynecology clinics of the University of Pennsylvania Health System, all patients receive a pelvic exam, measurement of post-void residual by bladder ultrasound, and administration of four urinary questionnaires as part of evaluation of urinary symptoms. The OABq-SF and the UDI-6 will be used to screen patients. Inclusion Criteria: adults aged 65 or older, urinary urgency of quite a bit severity or more on the Overactive Bladder Questionnaire-Short Form (OABq-SF),50 who are eligible for pharmacologic therapy for overactive bladder Exclusion Criteria: predominant stress incontinence (on UDI-6), current/recent use (6 m) or contraindication to anti-cholinergic medication, severe voiding difficulties, men on 5-alpha reductase inhibitors, severe neurologic disease, recent anti-incontinence or prolapse surgery, other urinary tract conditions such as calculus or recurrent UTI. Recruitment/Retention Experience: The urogynecology/urology clinics of the Hospital of University of Pennsylvania are high volume referral clinics staffed by four urogynecologists and one urologist. We see 125 female and 50 male patients with OAB per month with eligibility:participation ratio of 1.5:1 in clinical trials.42, 48, 51 In recent trials, 50% of recruited adults were Caucasian and 45% African-American. We anticipate that the female:male ratio will be 2:1. Recruitment : Pre-screening will occur at a patients routine visit, or via chart review following clinical care. If a patient appears to be eligible, they will be referred to the study coordinator to schedule a baseline visit. Patients of urogynecology or other referring geriatrics/urology/primary care practices may also self-refer for participation, as long as their medical records are available for eligibility determination. Baseline visit: At this visit, the trained coordinator will obtain informed consent, administer physical activity and other questionnaires (see Instrument and Testing Schedule below). Routine pre-treatment counseling on medical treatment, as well as counseling on additional non-medical (biofeedback, behavioral strategies, pelvic floor muscle training) and interventional treatments (neuromodulation), will also be provided. Then the coordinator will administer the Preference instrument on a bidirectional scale with 0 being undecided, and either extreme (5 or -5) being a strong preference for that particular treatment. The Short Physical Performance Battery (SPPB) test will also be performed with the oversight of trained personnel for safety. Accelerometers and instructions for wearing the accelerometer will be provided at that time. The monitor will be retrieved from the patient by a study coordinator or investigator 1 week later. Intervention: All subjects (irrespective of preference) will receive a 90-day supply of open label fesoterodine 4 mg per day. They will start medication 1 week after the baseline visit. After 4 weeks of treatment, dose may be increased to 8 mg over the telephone based on symptom report. This dosing regimen is direct alignment with clinical care. Change of prescription to another anti-cholinergic may occur during the study period, if determined necessary by the physician. Criteria that would warrant stopping fesoterodine include: - inability to tolerate common side effects, including dry mouth, dry eyes, and constipation - lack of satisfactory urinary symptom control on the highest dose of fesoterodine - immediate withdrawal in case of life-threatening side effects (uncommon, including angina, angioedema, diverticulitis, gastroenteritis, heat prostration, hypersensitivity reactions, irritable bowel syndrome, QT prolongation) Once withdrawn from fesoterodine, managing physicians would use their clinical judgment to switch the patient to another anti-cholinergic medication or switch to another class of medication (beta 3 agonist, or mirabegron). These patients would continue to be followed until after the 8 week follow-up visit, as the statistical plan will involve intention-to-treat analysis. The patients will continue to participate in the 8 week follow-up visit (including questionnaires and SPPB), regardless of whether or not they were switched to another medication. All adults will receive printed educational material on fluid modification, behavioral strategies, and Kegel exercises. 8 week follow up visit: One week prior, the study coordinator will once again provide subjects with accelerometers and instructions for wearing the accelerometer. At the 8 week visit, the patient will again complete self-administered physical activity, urinary symptoms, adherence, pill count, and neurocognitive instruments and tests with the oversight of a trained investigator (see Instrument and Testing Schedule below). The monitor will be retrieved from the patient by a study coordinator or investigator at the 8 week follow up visit. Instrument and Testing Schedule BASELINE VISIT: Urinary questionnaires (OABq-SF, UDI-6) Preference: Belief in Medication Questionnaire (BMQ), Bidirectional Visual Analogue Preference scale Physical activity:

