Analysis Plan Specific Aim 1 and 2: We will evaluate physical activity, adherence, and neurocognitive function before and after treatment to examine changes from baseline to 8 weeks in subjects with and without preference for medication. Concurrent validity, the relationship of the instrument to other similar evaluations, will be measured by comparing IPAQ, and CHAMPS scores to accelerometer data at baseline using the Spearman correlation coefficient and the intraclass correlation coefficient. Specifically, we will compare energy expenditure in MET*min/week (IPAQ) or MET*hour/week (CHAMPS) to that measured by the Actigraph accelerometer over the course of a week. For preference, we will compare subjects scores as indicated on the bidirectional scale to their necessity-harm differential as calculated by the Belief Screen of the BMQ using Spearman correlation coefficient. Contingency analyses tables will be used to determine the sensitivity and specificity of the bidirectional preference scale and the necessity-harm differential (as calculated on the Belief Screen) that best discriminates between those with preference for medication and those without. Discriminant validity, the ability to distinguish between populations, will be determined by comparing mean differences in energy expenditure for each physical activity instrument between responders and non-responders to anticholinergic medication as defined by the PGI-I. We will compare total MET*min/week (IPAQ) or MET*hour/week (CHAMPS), as well as energy spent in sedentary and moderate-to-vigorous physical activities (CHAMPS) between responders and non-responders using Wilcoxon rank sum test. For preference, we will compare the BMQ Belief necessity-harm differential and bidirectional preference scale score using Wilcoxon rank sum test. Responsiveness, the ability of the instruments to detect clinically meaningful change, will be assessed. First, pretreatment energy expenditure and preference will be compared with post-treatment activity and preference scores, respectively, using the t-test. Next, effect size (change in mean score/SD of baseline) and standardized response mean (change in mean score/SD of the change) will be assessed. For both, values of 0.50.7 will be considered moderate responsiveness; 0.81, good; and 1, excellent. We will measure minimum clinically important difference (MCID); specifically, the smallest change in physical activity associated with clinically meaningful change in global rating scale (mean change in energy expenditure in subjects indicating a little better or greater in the global rating scale). Specific Aim 3: We will compare within subject change in physical activity from baseline to 8 weeks using the paired t-test. Improvement in physical activity will be defined as 15% increase in energy expenditure as compared to baseline. The effect of age, comorbidities, baseline activity, severity of cognitive impairment, BMI on physical activity will be examined using regression analysis. We will also compare change in activity, proportion of subjects

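### The MCID is defined as a smallest meaningful change but computed as the mean over all improvers, and the pre-post preference statistics cannot be computed for the bidirectional scale, which is scheduled only at baseline

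*Combined protocol and SAP*

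**What the plan says.** **MCID.** One sentence of the Analysis Plan (Specific Aims 1 and 2) holds both a definition and a formula. The definition is "the smallest change in physical activity associated with clinically meaningful change in global rating scale". The formula, in parentheses, is the "mean change in energy expenditure in subjects indicating a little better or greater in the global rating scale". The sentence does not say which global scale is meant. The PGI-I is the only global rating scheduled, and its response grades are not listed.

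**Preference responsiveness.** The same paragraph says that "pretreatment energy expenditure and preference will be compared with post-treatment activity and preference scores, respectively, using the t-test". It adds that "effect size (change in mean score/SD of baseline) and standardized response mean (change in mean score/SD of the change) will be assessed". No preference instrument is named at that point. Elsewhere in the section two are in use: the bidirectional scale and the "necessity-harm differential as calculated by the Belief Screen of the BMQ".

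**Schedule.** Under Study Design (Design), the baseline visit text reads "Then the coordinator will administer the Preference instrument on a bidirectional scale with 0 being undecided", and the baseline entry in the Instrument and Testing Schedule is "Preference: Belief in Medication Questionnaire (BMQ), Bidirectional Visual Analogue Preference scale". The Procedures section repeats both instruments at baseline. At 8 weeks there is no preference heading. A BMQ follow-up form appears under adherence, and the bidirectional scale does not appear.

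**The concern.** The MCID formula does not estimate the quantity the definition describes. A smallest meaningful change is anchored on people who have only just improved. The planned mean also takes in everyone who improved by more. The calculation would run and return a number, so nothing in the output would reveal the mismatch. Potential Study Benefits says the instruments are being validated for later trials, so a mislabelled threshold could be carried into them.

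For preference, a pre-post comparison needs a post-treatment score. If one of the two instruments is never repeated, that part of the plan cannot be carried out on it, and the plan does not say which instrument was intended.

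**Working it through.** The documents state no MCID, effect size or standardized response mean, so there is no figure to reproduce. The check compares the text with the schedule and then illustrates the possible size.

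**1. MCID: definition against formula.** Let d be the step in mean activity change from one improved grade to the next, in SD of change. With three improved grades (an assumption), the pooled mean minus the *a little better* mean is

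share(grade 2) × d + share(grade 3) × 2d.

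For d = 0.2 and a 60/30/10 split: 0.30 × 0.2 + 0.10 × 0.4 = 0.06 + 0.04 = 0.10. The other entries follow in the same way.

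| Split of improvers (%) | d = -0.2 | d = 0 | d = +0.2 | d = +0.4 |
|---|---|---|---|---|
| 60/30/10 | -0.10 | 0 | 0.10 | 0.20 |
| 40/35/25 | -0.17 | 0 | 0.17 | 0.34 |
| equal thirds | -0.20 | 0 | 0.20 | 0.40 |
| 20/40/40 | -0.24 | 0 | 0.24 | 0.48 |

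The two means also coincide if the higher grades are empty or their differences cancel (for example +0.2 and -0.2 SD with equal thirds: (0.2 - 0.2)/3 = 0).

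**2. Precision of the narrower group.** The one input from the documents is the 68 evaluable subjects (Accrual, Sample Size, Specific Aim 1). Assume that 40%, 50% or 70% improve: 27.2, 34 and 47.6, or about 27, 34 and 48 subjects. The 95% CI half-width in SD is t(0.975, n - 1)/√n, with the same SD assumed in the pooled group and in each grade.

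| Improvers | Pooled half-width | *A little better* n (splits in the order above) | Half-width | Ratio to pooled |
|---|---|---|---|---|
| 27 | 0.396 | 16, 11, 9, 5 | 0.533, 0.672, 0.769, 1.242 | 1.35, 1.70, 1.94, 3.14 |
| 34 | 0.349 | 20, 14, 11, 7 | 0.468, 0.577, 0.672, 0.925 | 1.34, 1.65, 1.93, 2.65 |
| 48 | 0.290 | 29, 19, 16, 10 | 0.380, 0.482, 0.533, 0.715 | 1.31, 1.66, 1.84, 2.46 |

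Three of the twelve cases have fewer than 10 subjects in the *a little better* group.

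**3. Preference: what is measured when.**

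| Listing | Baseline | 8 weeks |
|---|---|---|
| Design, visit text | Bidirectional scale | Neither preference instrument named |
| Design, Instrument and Testing Schedule | BMQ, bidirectional scale | BMQ follow-up only |
| Procedures, visit items | BMQ, bidirectional scale | BMQ follow-up only |
| Procedures, Instrument and Testing Schedule | BMQ, bidirectional scale | BMQ follow-up only |

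The t-test, effect size and standardized response mean all need a post-treatment score. The bidirectional scale has none scheduled, so all three are undefined for it. For the BMQ they can be computed if the follow-up form repeats the baseline Belief Screen items. The documents do not say whether it does.

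**The case against.** The formula is an explicit, pre-stated rule. The mean in the *a little better* group is also an average rather than a literal minimum, so the contradiction could be removed by changing the label alone. The anchor scale is unnamed, and the proposed remedy needs a grade with that wording.

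The narrower estimate can also be the less accurate one. Take 27 improvers split 20/40/40 and a within-grade SD of 1. Scoring the grades 0, 1, 2 gives a variance of 0.56.

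- At d = 0.2 the pooled mean, used as an estimate of the *a little better* mean, has root-mean-square error √(0.24² + (1 + 0.04 × 0.56)/27) = 0.309. The single-grade mean has 1/√5 = 0.447.
- At d = 0.4 the order reverses: √(0.48² + (1 + 0.16 × 0.56)/27) = 0.520 against 0.447.

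The pattern is the same in all twelve cases: pooled is better at 0.2 SD and worse at 0.4 SD.

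On preference, the clause names no instrument. Procedures calls the BMQ the gold standard and it has an 8-week form, so on one reading the clause can be carried out as written.

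What stands: the anchor should be named, the precision cost is real, and the preference gap concerns one instrument only. What does not stand: an accuracy advantage that depends on an unknown gradient does not make the pooled mean the quantity defined. *A little better* is the plan's own grade label. Relabelling alone would be accurate, but it would leave the plan without an estimate of the minimal change it sets out to measure.

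**Conclusion.** The concern holds on both counts and is minor. The mismatch in the MCID sentence and the missing 8-week bidirectional scale are plain from the text. The size of the MCID error cannot be obtained from the documents. The illustrated range of -0.24 to +0.48 SD includes zero and rests on assumed grade numbers, splits and steps.

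The effect is confined to these reported results. Specific Aim 1 describes responsiveness as change before and after treatment and does not mention an MCID. Aim 2 asks about construct validity. The Aim 3 rule, "Improvement in physical activity will be defined as 15% increase in energy expenditure as compared to baseline", does not use the MCID, and the Aim 1 sample size rests on a correlation.

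**What to change.** **MCID.** Name the global scale and list its grades. Report two means under separate names:

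- the MCID, as the mean change in subjects rating exactly *a little better*, with a 95% CI and the no-change group shown for reference;
- the pooled value, as mean change among improvers.

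State in advance that if the *a little better* group is very small (for example fewer than 10, where the half-width is about 0.77 SD or more), its estimate is descriptive only and the pooled mean is still not called the MCID.

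**Preference.** Name the instrument in the pre-post clause. If 8-week visits are still open, add the bidirectional scale there and state how many subjects will have it. Otherwise limit the clause to the BMQ, provided its follow-up form repeats the baseline Belief Screen items, or delete the clause.

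**Cost.** The MCID change needs no new data. Under the assumptions above, the MCID would rest on about 5 to 29 subjects instead of 27 to 48. It is least precise when few improvers choose the lowest improved grade, which is also where the two means can differ most. Adding the scale is one item at an existing visit, but it would cover only subjects not yet seen at 8 weeks. Study duration planned for data collection to finish in September 2016 and the document is dated March 2018, so if visits are complete only the wording options remain.

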
Characteristics of the Study Population

Target population

Adult subjects aged 65 or older with overactive bladder undergoing treatment with medication

Subjects enrolled by Penn Researchers

80

Subjects enrolled by Collaborating Researchers

0

Accrual

Recruitment/Retention Experience: The urogynecology/urology clinics of the Hospital of University of Pennsylvania are high volume referral clinics staffed by four urogynecologists and one urologist. We see 125 female and 50 male patients with OAB per month with eligibility:participation ratio of 1.5:1 in clinical trials. In recent trials, 50% of recruited adults were Caucasian and 45% African-American. We anticipate that the female:male ratio will be 2:1. Sample Size: Specific Aim 1: A sample size of 68 evaluable subjects will provide 90% power to detect a correlation coefficient of 0.72 or greater, assuming a correlation coefficient of 0.5 or less between the physical activity questionnaires and the criterion standard (accelerometer) is undesirable (null hypothesis). Assuming a 15% loss to follow-up, we plan to enroll 80 patients to ensure an adequate sample of at least 68 subjects with complete datasets. Specific Aim 2: We have conservatively assumed that 50% subjects will express preference for medication. Prior Penn studies show 56% adherence at 8 weeks in unselected subjects. Assuming that adherence will be 80% in subjects expressing preference for medication, a sample size of 80 subjects will provide 90% power to demonstrate a 30% difference in adherence rates in subjects who do or do not have preference for medication. Specific Aim 3: Assuming two-tailed alpha of 0.05, a sample size of 80 subjects will provide 90% power to show a 30% difference in physical activity in the proportion of subjects expressing preference for medication versus those without preference.

Key inclusion criteria

Inclusion Criteria: adults aged 65 or older, urinary urgency of quite a bit severity or more on the Overactive Bladder Questionnaire-Short Form (OABq-SF),⁵⁰ who are eligible for pharmacologic therapy for overactive bladder

Key exclusion criteria

Exclusion Criteria: predominant stress incontinence (on UDI-6), current/recent use (6 m) or contraindication to anti-cholinergic medication, severe voiding difficulties, men on 5-alpha reductase inhibitors, severe neurologic disease, recent anti-incontinence or prolapse surgery, other urinary tract conditions such as calculus or recurrent UTI.

Vulnerable Populations

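### Aim 3 attaches its 90% power to a difference in a proportion, which reaches that power only at extreme base rates and is weaker than the continuous comparison already listed; no primary Aim 3 test is named

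*Combined protocol and SAP*

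**What the plan says.** The Accrual section, under Sample Size for Specific Aim 3, states that "a sample size of 80 subjects will provide 90% power to show a 30% difference in physical activity in the proportion of subjects" with a preference for medication, "versus those without preference". The test level is given: "Assuming two-tailed alpha of 0.05". No base rate, SD or test is stated, and the instrument is not named.

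The Analysis Plan for Specific Aim 3 contains the only definition of success for activity: "Improvement in physical activity will be defined as 15% increase in energy expenditure as compared to baseline". It does not justify the 15% or say whether it applies to the accelerometer, IPAQ or CHAMPS.

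The same section lists several Aim 3 analyses without ranking them:
- a paired t-test of within-subject change;
- change in activity compared by preference;
- the share improved compared by preference;
- a regression for the effect of preference, adjusted for baseline activity, comorbidity index, age and BMI. Its outcome is not stated.

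Two further inputs stand under the other aims. For Aim 2: "We have conservatively assumed that 50% subjects will express preference for medication". For Aim 1: "Assuming a 15% loss to follow-up, we plan to enroll 80 patients", which leaves 68 evaluable.

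**The concern.** Cutting a continuous change at 15% discards information. A subject who gains 16% counts the same as one who gains 80%, and one who gains 14% counts the same as one who declines. If the stated power belongs to that proportion, the study has been sized on the weaker of two comparisons it intends to make from the same data. The power of a proportion also depends on the base rate, which is missing, and on the number evaluable, which the Aim 3 sentence takes as all 80.

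Two things are at stake. A real effect of preference on activity could be missed by the comparison that carries the power claim. And with no primary test named, the main Aim 3 result could be chosen after the estimates are known.

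**Working it through.** **Inputs.** From the Accrual section: N = 80, power 90%, difference 30 points, two-sided alpha 0.05, equal split (stated for Aim 2, assumed here for Aim 3) and 15% loss. So n = 40 per group, or 80 × 0.85 / 2 = 34 per group evaluable. Not in the documents, and so varied: the base rate p without preference, and the weekly within-person CV.

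**Step 1. The plan's 90%.** For p v q = p + 0.30, with m = (p + q)/2, the pooled normal approximation is

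power = Φ{ [0.30√n − 1.96√(2m(1−m))] / √(p(1−p) + q(1−q)) }.

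At 20% v 50% with n = 40: (1.897 − 1.322)/0.640 = 0.898, so power is 82%. With n = 34: (1.749 − 1.322)/0.640 = 0.667, so 75%. Other base rates:

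| p v q | n = 40 | n = 34 |
|---|---|---|
| 2% v 32% | 96% | 93% |
| 5% v 35% | 93% | 89% |
| 8% v 38% | 91% | 85% |
| 10% v 40% | 89% | 83% |
| 20% v 50% | 82% | 75% |
| 35% v 65% | 78% | 70.5% |
| 50% v 80% | 82% | 75% |
| 60% v 90% | 89% | 83% |

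The plan's figure cannot be reproduced without a base rate. With all 80 evaluable it is met at about 10% v 40% or more extreme, or the mirror image. With 68 evaluable it needs a base rate below 5%, or the mirror image.

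**Step 2. Continuous change for the same effect.** Assume change is normal with equal SD in both groups, and that preference shifts the mean by enough to give the same 30-point gap at the cut. The shift in SD units is d = z(q) − z(p), where z is the normal quantile. Power comes from the two-sample t-test (noncentral t, noncentrality d√(n/2)).

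At 20% v 50%, d = 0 + 0.842 = 0.842. With n = 40 the noncentrality is 0.842 × √20 = 3.76 against a critical value of 1.99, giving 96%. At 35% v 65%, d = 0.385 + 0.385 = 0.771.

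| p v q | n | Proportion | Continuous |
|---|---|---|---|
| 10% v 40% | 40 | 89% | 99.5% |
| 20% v 50% | 40 | 82% | 96% |
| 35% v 65% | 40 | 78% | 93% |
| 20% v 50% | 34 | 75% | 93% |
| 35% v 65% | 34 | 70.5% | 88% |

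Total N for 90% power, proportion v continuous: 84 v 42 at 10% v 40%, 104 v 62 at 20% v 50%, 114 v 74 at 35% v 65%. Any gain from baseline adjustment is not counted.

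**Step 3. Where 15% sits relative to weekly variation.** Accelerometer activity is taken from single weeks ("that measured by the Actigraph accelerometer over the course of a week"). For two independent log-normal weeks with no true change, the SD of the log ratio is √(2 ln(1 + CV²)), and the share flagged as improved is 1 − Φ(ln 1.15 / SD). At CV 10%: SD = 0.141, 0.1398/0.141 = 0.99, share 16%.

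| Assumed weekly CV | Unchanged subjects flagged |
|---|---|
| 5% | 2% |
| 10% | 16% |
| 20% | 31% |
| 30% | 37% |

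The documents give no variability figure, so this is a range and not a finding.

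**The case against.** **The continuous analyses are already there.** This is correct, and it limits the point. Change by preference and the baseline-adjusted regression are both planned, so the continuous information would not be lost. What remains is that the power statement is worded for a proportion, the regression's outcome is not stated, and nothing is ranked.

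**The link to the 15% rule is an inference.** This also stands. The sample-size sentence is unclear and does not cite the rule. But a difference in proportions needs a definition of success, and the plan has only one for activity.

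**Aim 3 is preliminary.** The Objectives say that it will supply preliminary data. That lowers the stakes, but the plan still makes an explicit 90% claim for it.

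Three stronger readings are tempting, and the documents do not support them.
- A reader might infer that 15% lies inside week-to-week noise. Step 3 shows that this depends wholly on the CV, and one CV cannot stand for the accelerometer and both questionnaires.
- A reader might infer that misclassification would shrink the planned 30-point gap and that a continuous analysis would win the power back. If the 30% means measured improvers, misclassification is already in it. If instead subjects are a mixture of unchanged and truly +30%, with a 30-point difference in the share of changers, 34 per group and an assumed CV of 25%, power is about 11% for the proportion and 14% for continuous change. The continuous analysis barely helps there. The advantage in Step 2 belongs to the shift model.
- A reader might want the study's own minimum important difference in place of 15%. It is estimated from the same subjects, so the cut would be data-driven, whereas 15% is fixed in advance.

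**Conclusion.** The point holds as one about how Aim 3 is sized and which of its comparisons leads. With 40 per group, dichotomising costs about 14 to 15 percentage points of power at 20% v 50% and 35% v 65%. With 34 per group it costs about 17 to 18. The stated 90% is not delivered for the proportion at 68 evaluable unless the base rate is below 5%, or its mirror image.

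This rests on an equal preference split, on reading the 30% as percentage points of subjects improved, and on a normal shift with equal SD for the continuous comparison. The shortfall in the proportion's own power does not need the shift model. That 15% falls within weekly variation is possible but unproven, and the verdict does not depend on it.

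**What to change.** In the Analysis Plan, name one primary Aim 3 comparison: the baseline-adjusted regression already planned, with log energy expenditure at week 8 as its outcome, on one named instrument, and with a stated rule for zero scores, since a zero has no logarithm.

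In the Accrual section, restate Aim 3 power for that comparison on 68 evaluable subjects and give the assumed SD and its source. As a guide, before any gain from adjustment, 34 per group gives 90% power for a difference of 0.80 SD (0.73 SD with 40 per group).

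Keep the share with a 15% rise as secondary and descriptive, and give a reason for the 15%.

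The cost is wording in two sections, with no new data or visits. There is one small downside: the main result becomes a ratio of energy expenditure between groups, which is less immediate for clinical readers than a percentage of improvers. The secondary result still supplies that percentage.
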